7.4 Loss of Participants to Follow-Up

A participant will be considered lost to follow-up if he or she is unable to be contacted by the study site. The following actions must be taken if a participant cannot be contacted at Day 14 or Day 28:

- The site must attempt to contact the participant and counsel the participant on the importance of maintaining the assigned schedule and ascertain whether or not the participant wishes to and/or should continue in the study.
- In cases in which the participant is deemed lost to follow-up, the Investigator or designee must make every effort to regain contact with the participant (where possible, three telephone calls and, if necessary, a certified letter to the participant's last known mailing address or local equivalent methods). These contact attempts should be documented in the participant's medical record/CRF.
- Should the participant continue to be unreachable, he/she will be considered to have withdrawn from the study.

8 Study Assessments and Procedures

Study procedures and their timing are summarized in the SoA (Table 1-1). Protocol waivers or exemptions are not allowed.

Immediate safety concerns should be discussed with the Sponsor immediately upon occurrence or awareness to determine if the participant should continue or discontinue study intervention.

Adherence to the study design requirements, including those specified in the SoA, is essential and required for study conduct.

All screening evaluations must be completed and reviewed to confirm that potential participants meet all eligibility criteria. The Investigator will maintain a screening log to record details of all participants screened and to confirm eligibility or record reasons for screening failure, as applicable.

Procedures conducted as part of the participant's routine clinical management (e.g., blood count) and obtained before signing of the ICF may be utilized for screening or baseline purposes provided the procedures met the protocol-specified criteria and were performed within the time frame defined in the SoA (Table 1-1).

The maximum amount of blood collected from each participant over the duration of the study, including any extra assessments that may be required, will not exceed 20 mL.

Repeat or unscheduled samples may be taken for safety reasons or for technical issues with the samples.

Informed Consent

Informed consent must be documented according to Appendix 1, Section 10.1.3.

Eligibility Criteria

All inclusion and exclusion criteria will be reviewed by the Investigator or designee to ensure that the participant qualifies for the study.

Participant Identification Card

All participants will be given a participant identification card identifying them as participants in a research study. The card will contain study site contact information (including direct telephone numbers) to be used in the event of an emergency. The Investigator or qualified designee will provide the participant with a participant identification card immediately after the participant provides written informed consent. At the time of intervention allocation/randomization, site personnel will add the intervention/randomization number to the participant identification card.

Medical History

A medical history will be obtained by the Investigator or qualified designee. The medical history will collect all active conditions and any condition diagnosed that the Investigator considers to be clinically relevant. Details regarding the disease for which the participant has enrolled in this study will be recorded separately and not listed as medical history.

Prior and Concomitant Medications Review

The Investigator or qualified designee will review prior medication use and record prior medications taken by the participant within 3 months prior to screening. This should include a history of hypertension medication, in particular angiotensin-converting enzyme inhibitors and angiotensin receptor blockers.

The Investigator or qualified designee will record medication, if any, taken by the participant during the study through the last assessment. Concomitant medications will be recorded on an ongoing basis during the study (or longer if related to an SAE).

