AE/SAE review	X	X	X	X	X	X	X	
Concomitant medication review	X	X	X	X	X	X	X	
Oxygen / respiratory assessment ⁷	X	X	X	X				
SpO ₂ on room air (after at least 1 minute) prior to study intervention administration and immediately at the end of nebulization ⁶		X	X	X				See Section 8.1.2
Modified WHO ordinal scale	X	X	X	X		X	X	See Section 8.1.1

Procedure	Screening (up to 48 hours before Day 1 ¹)	Intervention Period			Early withdrawal	Efficacy follow-up (Day 14) ² (± 2 days)	EoS efficacy and safety follow-up (Day 28) ² (± 2 days)	Notes
		Day 1 ¹	Daily while hospitalized	Day 10 / hospital discharge				
NEWS 2 assessment ⁷		X	X	X				Prior to study intervention in the morning. See Section 8.1.3

Abbreviations: AE=adverse event; aPTT= activated partial thromboplastin time; CBC=complete blood count; Chem 7=blood chemistry panel (sodium, potassium, chloride, bicarbonate/CO₂, blood urea nitrogen, creatinine, glucose); CV=cardiovascular; ECG=electrocardiogram; LFTs=liver function tests; mHb=methemoglobin; PT/INR=prothrombin time/international normalized ratio; RT-PCR=reverse transcription-polymerase chain reaction; SAE=serious adverse event; TID=three times daily.

1. Screening and randomization may be on the same day, providing all eligibility criteria are met.
2. For participants who are already discharged at either the Day 14 or Day 28 (EoS) follow-up, there will be a phone call to check AEs/SAEs, concomitant medications, and modified WHO ordinal scale. At EoS, safety laboratory tests (nitrite and mHb only) and weight will be collected for participants in hospital only.
3. COVID-19 infection must be confirmed and documented in chart with a positive result on a validated test.
4. At Screening: CBC, chem 7, mHb, LFTs, coagulation (PT/INR, aPTT).
On Day 1, Day 3, Day 7 and Day 10, or early withdrawal: CBC and chem 7 (per SOC).
On Day 28: nitrite and mHb (participants in hospital at EoS only).
5. Vital signs: temperature, heart rate, blood pressure, respiratory rate. Vital signs to be repeated as per SOC during treatment period.
6. Study intervention comprises the following procedures which are to be done in order and as quickly as possible:
 - a. Recording of oxygen flow level including mode (nasal cannula, mask)
 - b. Recording of SpO₂ and heart rate
 - c. Discontinuation of supplemental oxygen administration *
 - d. Close participant oversight by trained health care professional until SpO₂ is stable on ambient air after one minute at least *

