7.3 Participant Discontinuation/Withdrawal from the Study

A participant may withdraw from the study at any time at his/her own request or may be withdrawn at any time at the discretion of the Investigator for safety, behavioral, or

administrative reasons. The participant will be definitively discontinued from both the study intervention and from the study at that time.

If the participant withdraws consent for disclosure of future information, the Sponsor may retain and continue to use any data collected before such a withdrawal of consent.

If a participant withdraws from the study, he/she may request destruction of any samples taken and not tested, and the Investigator must document this in the site study records.

At the time of discontinuing from the study, if possible, an early discontinuation assessment should be conducted, as shown in the SoA (Table 1-1).

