9.4.1 General Considerations

All statistical analyses will be conducted using SAS, Version 9.4 or later. Baseline characteristics will be summarized by treatment arm. For continuous measures the mean and standard deviation (SD) will be summarized. Categorical variables will be described by the proportion in each category. In addition, 95% confidence intervals (CIs) will be computed as indicated.

All the categorical variables including the primary endpoint will be summarized by treatment with the numbers and percentages of the participants. Treatment difference will be tested using a Cochran–Mantel–Haenszel test stratified by 1) country and 2) participant's clinical status at Baseline. For the categorical endpoints, relative risk and its 95% CI will be presented.

All of the continuous variables, including the changes from Baseline, will be summarized by treatment with the means, SD, medians and the ranges. The mixed model with repeated

measurements /analysis of covariance model with treatment, country, participant's clinical status at Baseline and visit as the model term, and Baseline value as the covariate will be used to test for the significance of the treatment difference. Least square means, standard errors, 95% CIs and p-values will be presented.

Time to event endpoints will be analyzed using the Cox Proportional Hazard model with treatment, participant's clinical status at Baseline and country as the model term. The hazard ratio of RESP301+SOC versus SOC will be presented along with 95% CI and p-value from the model. The Kaplan-Meier curves of the time to events will be presented by treatment for each applicable endpoint.

Handling of missing data

If participants are discharged from the hospital prior to Day 14 due to improvement of the clinical status and their status on Day 14 cannot be obtained, their status on Day 14 for the primary endpoint will be imputed with the status on the day of discharge. Depending on the reasons for missing data on the primary endpoint up to Day 14, additional sensitivity analyses will be performed. Further details on handling on missing data will be provided in the SAP.

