9.4.2 Primary Endpoint

The primary endpoint is the proportion of participants who progress to level >4 of the modified WHO ordinal scale due to COVID-19 by Day 14.

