9.4.3 Secondary Endpoint(s)

The key secondary endpoints are:

1. Change from baseline on the modified WHO ordinal scale at each visit up to Day 28
2. Change in room air SpO₂ from baseline over time
3. Change in NEWS 2 symptom score from baseline over time
4. Time to improvement to a lower level (<4) of the modified WHO ordinal scale
5. Time to progression to a higher level (>4) of the modified WHO ordinal scale

Additional secondary endpoints are:

1. Time to hospital discharge
2. Incidence of mortality by Day 28

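### Participants who cannot be reached after discharge are treated as withdrawn, no vital-status or readmission check is required, and their Day 14 outcome defaults to non-progression

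*Protocol*

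**What the plan says.** After discharge, the Schedule of Activities (Section 1.3, footnote 2) collects outcome at Day 14 and Day 28 by telephone: "there will be a phone call to check AEs/SAEs, concomitant medications, and modified WHO ordinal scale".

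If the participant cannot be contacted at either time, Section 7.4 requires documented attempts ("where possible, three telephone calls and, if necessary, a certified letter to the participant's last known mailing address", or local equivalents). If these fail: "Should the participant continue to be unreachable, he/she will be considered to have withdrawn from the study". Section 7.3 says of withdrawal at the participant's request or the investigator's discretion: "The participant will be definitively discontinued from both the study intervention and from the study at that time".

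Section 4.1 takes a different line for participants who stop treatment early, including those who improve to level 1 or 2. They remain in the study up to the Day 28 safety call, and before Day 10 only withdrawal of consent counts as early withdrawal.

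On the outcome, Section 9.4.2 states: "The primary endpoint is the proportion of participants who progress to level >4 of the modified WHO ordinal scale due to COVID-19 by Day 14". Death is level 7 of that scale. Section 9.4.3 adds "Incidence of mortality by Day 28" as a secondary endpoint. For a participant discharged because of improvement whose Day 14 status is unobtainable, Section 9.4.1 says "their status on Day 14 for the primary endpoint will be imputed with the status on the day of discharge". It also says: "Depending on the reasons for missing data on the primary endpoint up to Day 14, additional sensitivity analyses will be performed".

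**The concern.** Every contact step that Section 7.4 prescribes is aimed at the participant. Someone who has died at home, or is ventilated in another hospital, cannot answer a call or a letter. The outcome can therefore cause the loss of contact, and that outcome is exactly what the primary endpoint and Day 28 mortality count.

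The rules then act in one direction. The participant is closed out as withdrawn, no other source has to be consulted, and the primary endpoint is filled with a discharge status that is by construction below level 5. A true event can become a success. This is a data-collection gap: an analysis plan can vary the assumption about these participants, but it cannot recover an outcome that nobody was asked to look for.

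**Working it through.** **The passages side by side**

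1. Unreachable at Day 14 leads to withdrawn (7.4). Whether the Day 28 call is still due is not stated: 7.3 suggests not, while 4.1 suggests that it is for those who stopped treatment because they improved.
2. Sections 9.3 and 10.5.1 promise follow-up to the primary endpoint after withdrawal from treatment. Neither addresses loss of contact.
3. Safety reporting is partial cover. A caregiver may report adverse events (8.3), and rehospitalization of someone discharged during treatment is a seriousness criterion (10.4.2). But 10.4.2 gives death from disease progression as an example of what is not an SAE, and 8.3.1 does not oblige investigators to seek events once participation has ended.
4. Section 10.5.1 itself finds the discharge imputation text unclear and asks for further discussion. It also says that interim participants not yet followed for 14 days must not be imputed as non-progressed, because their outcome is unknown. The same logic applies here.

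**The plan's own figure**

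Inputs (Sections 9.2 and 9.5): 30% versus 15%, 100 control and 200 RESP301, one-sided 0.025 (0.0249 at the final analysis), about 80% power. With mean rate (0.30 + 2 × 0.15)/3 = 0.20, the uncorrected control-arm size is [1.960√(1.5 × 0.20 × 0.80) + 0.842√(0.30 × 0.70 + 0.15 × 0.85/2)]²/0.15², which rounds up to 88, or 264 in total. With continuity correction it is 97, or 291 in total (294 at 0.0249). Power at 100/200 and 0.0249 is 81.2% with continuity correction and 81.4% by Fisher's exact test. The stated 300 reproduces.

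**How many events could be lost (all three rates are assumptions)**

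- Unreachable: 300 × (0.50 to 0.65 discharged by Day 14) × (0.05 to 0.10 not reached) = 7.5 to 19.5.
- Dead or readmitted above level 4: × (0.10 to 0.25) = 0.8 to 4.9, so about 1 to 5, against 30 + 30 = 60 planned primary events.

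This count has no Day 14 limit and no attribution to COVID-19, so it is generous for the primary endpoint.

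**Effect on the final test**

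Pooled z = (p_C − p_T)/√[p̄(1 − p̄)(1/100 + 1/200)], critical value 1.962.

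| Control | RESP301 | z |
|---|---|---|
| 30/100 | 30/200 (planned) | 3.06 |
| 30/100 | 35/200 (five added, all RESP301) | 2.48 |
| 30/100 | 39/200 | 2.04 |
| 30/100 | 40/200 | 1.93 |

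Losing the planned result takes 40 − 30 = 10 extra events, all in RESP301, which is twice the upper assumed figure.

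**Worst-case bounds**

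The planned rates leave 70 control and 170 RESP301 non-progressors. Suppose a fraction of these is unreachable and all of them are counted as progressed (planned result: one-sided p = 0.0011):

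| Unreachable | Control / RESP301 | p, both arms recoded | p, RESP301 only recoded |
|---|---|---|---|
| 2% | 1.4 / 3.4 | 0.0018 | 0.0039 |
| 5% | 3.5 / 8.5 | 0.0032 | 0.018 |
| 10% | 7 / 17 | 0.0070 | 0.11 |

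**If events are missed in one arm only**

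With a true 30% in both arms, missing 1, 2 or 3 percentage points in RESP301 only (2, 4 or 6 of 200 participants) raises one-sided type I error from 0.0249 to about 0.038, 0.056 and 0.080.

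**The case against.** The strongest reply is that the protocol does not give up lightly. Section 7.4 demands every effort, three calls where possible, a letter or local equivalent, and documentation; withdrawal comes last. Section 4.1 keeps improved participants in the study to Day 28. The sentence quoted from 7.3 is written for withdrawal by choice or by investigator decision, not for lost contact. Nothing forbids a records check, a site may learn of a readmission to its own hospital, and the imputation applies only where Day 14 status cannot be obtained. Sensitivity analyses are promised, with details left to the SAP.

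Most of this stands and limits the point. It does not close it: no passage requires anyone to look beyond the participant, and a promised sensitivity analysis cannot supply an unobserved death.

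Three stronger readings are tempting, and the documents do not support them:

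- A reader might infer that lost participants drop out of Day 28 mortality. The ITT population keeps all randomized participants (9.3), and how unknown vital status is counted may be left to the SAP. What follows from the protocol is that such deaths can go unrecorded.
- A reader might infer that one lost event can decide the trial. That is true only at the step from 39 to 40 of 200, and any binary test has such a step.
- A reader might infer bias towards whichever arm discharges earlier. Open-label treatment makes that possible, but no passage shows a difference between arms.

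**Conclusion.** The point holds as a gap in outcome ascertainment that is cheap to close. Followed as written, Sections 1.3, 7.4 and 9.4.1 together can score a post-discharge death or ventilation as non-progression and leave a death by Day 28 unrecorded, and 7.4 needs reconciling with 4.1 for participants lost at Day 14.

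Its size cannot be derived from the documents. Under the assumed rates it is about 1 to 5 events. The planned result survives that, and also survives counting every unreachable participant in both arms as progressed at 10% loss (p = 0.0070). It fails only in the one-sided extreme of 10% loss with RESP301 alone recoded (p = 0.11). The gap therefore matters if the observed result lies near the boundary or if loss differs by arm. Even with equal loss, Day 28 mortality could be understated.

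The Section 7.4 text relied on is that of Version 2.0. The Amendment 2 change table lists no change to that section, but the amended section itself is not in the material available.

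**What to change.** - **Section 7.4:** reserve the term withdrawn for withdrawal of consent, and reconcile the section with 4.1. State that the Day 28 contact is attempted whatever happened at Day 14.
- **Consent and enrolment:** record an alternate contact and, where permitted, permission to consult hospital records. For anyone unreachable, ascertain vital status and any readmission or ventilation up to Day 14 and up to Day 28 from those records or that contact.
- **Section 9.4.1:** apply the discharge-status imputation only when that search was completed and found no event. Treat the remainder as missing, and add a prespecified sensitivity analysis that counts them as progressed.

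The cost is protocol wording, one contact field, and a records check for a small number of participants (8 to 20 under the assumed rates).

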8.1 Efficacy Assessments

8.1.1 Modified WHO Ordinal Scale

A modified WHO ordinal scale will be used for consistency with the recent study of lopinavir-ritonavir in adults hospitalized with severe COVID-19 (Cao et al, 2020), to record the participant's status at the time of assessment. The modified WHO ordinal scale includes the following levels:

1. Not hospitalized, no limitations on activities;
2. Not hospitalized, limitation on activities;
3. Hospitalized, not requiring supplemental oxygen;
4. Hospitalized, requiring supplemental oxygen;
5. Hospitalized, on non-invasive ventilation or high-flow oxygen devices;
6. Hospitalized, on invasive mechanical ventilation or extra corporeal membrane oxygenation (ECMO);
7. Death.

8.1.2 Pulse Oximetry

Pulse oximetry measurements will be performed to evaluate SpO₂ as outlined in the SoA (Table 1-1) and in accordance with the site standard operating procedures, on a medical-grade medical device. Measurements will be taken with a probe on fingertip or earlobe and recorded as percent oxygenated hemoglobin. Supplemental oxygen used at the time of assessment and method of oxygen delivery will be collected and documented along with the SpO₂.

Prior to administration of study intervention, supplemental oxygen will be held for at least a minute and SpO₂ checked in order to ensure participant may safely receive the study intervention. For safety reasons, since due to the current pandemic it cannot be guaranteed that study intervention will be consistently administered under direct medical supervision, the study Investigators should provide study personnel who are able to monitor the participant and their SpO₂ and ensure that should it decrease to a threshold, this would trigger immediate discontinuation. By default, unless overruled by the study Investigator, this SpO₂ threshold is set to 89%. This threshold should be entered into the saturation monitoring device to trigger an alarm during nebulization.

FiO₂ will be measured per site standard practice and recorded in the eCRF. The device used to administer oxygen should also be recorded.

8.1.3 National Early Warning Score (NEWS) 2

The NEWS 2 will be measured prior to study intervention in the morning according to the SoA in Table 1-1.

The NEWS is based on a simple aggregate scoring system in which a score is allocated to physiological measurements, already recorded in routine practice, when patients present to, or are being monitored in hospital (RCP, 2012). Six simple physiological parameters form the basis of the scoring system:

1. Respiration rate
2. Oxygen saturation
3. Systolic blood pressure
4. Pulse rate
5. Level of consciousness or new confusion*
6. Temperature

**The patient has new-onset confusion, disorientation and/or agitation, where previously their mental state was normal – this may be subtle. The patient may respond to questions coherently, but there is some confusion, disorientation and/or agitation. This would score 3 or 4 on the Glasgow Coma Scale (rather than the normal 5 for verbal response), and scores 3 on the NEWS system.*

A score is allocated to each parameter as they are measured, with the magnitude of the score reflecting how extremely the parameter varies from the norm (zero for ‘normal’; maximum

score 3). The score is then aggregated. The score is increased by 2 points for people requiring supplemental oxygen to maintain their recommended oxygen saturation. This is a pragmatic approach, with a key emphasis on system-wide standardization and the use of physiological parameters that are already routinely measured in National Health Service (NHS) hospitals and in prehospital care, recorded on a standardized clinical chart – the NEWS 2 chart (Refer to Appendix 2: The NEWS 2 Scoring System).

Reproduced from: Royal College of Physicians. National Early Warning Score (NEWS) 2: Standardising the assessment of acute-illness severity in the NHS. Updated report of a working party. London: RCP, 2017 (RCP, 2017).

8.2 Safety Assessments

Planned time points for all safety assessments are provided in the SoA (Table 1-1).

8.2.1 Physical Examinations

A complete physical examination will include, at a minimum, assessments of the head/ear/eyes/nose/throat, cardiovascular, respiratory, gastrointestinal, lymphatic, skin and neurological systems. Height (screening only) and weight will also be measured and recorded.

A brief physical examination will include, at a minimum, assessments of the skin, lungs, cardiovascular system, and abdomen (liver and spleen).

